計畫書英文摘要 (Protocol Synopsis)	文件編碼	KMUH/IRB/SOP/02.01.O
		版次	2024.00

I. Protocol title: Effects of an Exercise Snack Intervention on Employee Health and Work Performance: A Study at Kaohsiung Medical University

II. Objectives:

- (1) To develop brief exercise videos targeting different areas of physical discomfort (e.g., neck and shoulders, lower back, lower limbs), specific fitness goals (e.g., localized muscle stretching, targeted muscle strengthening, cardiorespiratory endurance, balance training), high-intensity interval training (HIIT), or the acquisition of specific movement skills (e.g., core stability, pelvic floor muscle contraction, and multi-directional pelvic mobility).
- (2) To design personalized exercise "menus" based on individual needs identified through a preliminary assessment, with the goal of improving adherence to voluntary exercise routines among staff.
- (3) To apply the concept of "exercise snacking" by implementing a daily routine of 3 to 8 brief exercise sessions, and to evaluate changes in staff members' physiological health, work performance, and exercise behavior after a 12-week intervention.

III. Test drug

1. **Name:** Not applicable
2. **Dosage form:** Not applicable
3. **Dose(s):** Not applicable
4. **Dosing schedule:** Not applicable
5. **Mechanism of action:** Not applicable
6. **Pharmacological category:** Not applicable

IV. Study design

1. **Control:** placebo
 - active (please specify name and dosage)
 - others

■ Uncontrolled
2. **Blinding:** open-label single blind double blind others
3. **Randomized:** yes no
4. **Parallel** cross-over others
5. **Sample/Data**
 - Biospecimens(IF sourced from the biological database No Yes , Name :)
 - Excluding DNA extraction
 - Including DNA extraction

	計畫書英文摘要 (Protocol Synopsis)	文件編碼	KMUH/IRB/SOP/02.01.O
		版次	2024.00

Medical record data

Questionnaires

Record (including measurements, interviews, voice recordings, video recordings)

Big data

Others: _____

6. Duration of study: from IRB approval ~to 12, 31, 2028, total 43 months

Duration of Enrollment: from IRB approval ~to 12, 31, 2028, total 43 months

Duration of treatment: from IRB approval ~to 12, 31, 2028, total 43 months

Duration of follow-up: from IRB approval ~to 12, 31, 2028, total 43 months

7. Multi-national multi-center(Taiwan) single center(Taiwan)

8. Number of subjects:

9. Is there any of the followings included DSMB, Data Safety Monitoring Board:

yes no

V. Assessment criteria

1. Efficacy: Physical fitness assessments, Performance on functional movement tasks

2. Safety: Not applicable

3. Pharmacokinetics: Not applicable

4. Quality of life: Perceived stress scale, Work performance, Burnout inventory

VI. Selection criteria

1. Main inclusion criteria:

- (1) Currently employed at Kaohsiung Medical University or Kaohsiung Medical University Hospital.
- (2) Willing to participate in a 12-week exercise intervention, complete related questionnaires, and undergo physical performance assessments.

2. Main exclusion criteria:

- (1) Pregnant individuals, due to safety concerns related to exercise intensity and physical assessments.
- (2) Individuals with a diagnosed neurological disorder (e.g., stroke, Parkinson's disease).
- (3) Individuals experiencing severe pain in the upper or lower limb joints that interferes with their ability to complete the assessments.
- (4) Individuals assigned to high-intensity exercise who have unstable cardiac conditions (e.g., angina, myocardial infarction, heart failure).

	計畫書英文摘要 (Protocol Synopsis)	文件編碼	KMUH/IRB/SOP/02.01.O
		版次	2024.00

VII. Study procedures(summary)

1. Written informed consent must be obtained before any study specific procedures are undertaken.
 - (1) Recruitment announcements will be distributed through internal communication channels at Kaohsiung Medical University and its affiliated hospital.
 - (2) An introductory session and practical workshop on the "exercise snacking" program will be held.
 - (3) Participants will complete the informed consent form and attend a brief interview to complete questionnaires, including basic information (e.g., exercise habits) and a "personal issues and exercise needs assessment" to assist in designing a personalized exercise menu.
2. The process of the experiment (brief describe)
 - (1) Pre-intervention assessment: Participants will undergo baseline testing within one week prior to the start of the exercise intervention.
 - (2) Intervention period: Participants will engage in a 12-week exercise intervention program.
 - (3) Post-intervention assessment: Within one week following the intervention, participants will complete follow-up assessments.
 - (4) Follow-up check: One month after the completion of the program, participants will be contacted to assess whether they have continued engaging in the exercises independently without supervision from the research team.

VIII. Concomitant treatment:

1. Permitted: Not applicable
2. Prohibited: Not applicable

IX. Statistical analysis

1. Statistical Method for Efficacy / Safety measurements:

This study adopts a cross-sectional data collection approach, and all data analyses will be conducted using SPSS version 20. The normality of continuous variables will be assessed using the One-Sample Kolmogorov-Smirnov test. Based on the results of the normality test, appropriate statistical methods will be selected.

If the data are normally distributed, parametric tests such as the paired-sample t-test will be used to compare pre- and post-intervention differences. If the data are not normally distributed, non-parametric tests such as the Wilcoxon signed-rank test will be employed.

Additionally, correlations between variables will be analyzed using either Pearson's correlation

	計畫書英文摘要 (Protocol Synopsis)	文件編碼	KMUH/IRB/SOP/02.01.O
		版次	2024.00

coefficient (for normally distributed data) or Spearman's rank correlation coefficient (for non-normally distributed data).

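### The synopsis enters safety as not applicable for a 12-week exercise programme that can include high-intensity training, and shows no outcome or question that would count adverse events

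*Protocol*

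**What the plan says.** - **Assessment criteria.** Section V, item 2 reads "Safety: Not applicable". Item 1 (efficacy) names physical fitness and functional movement. Item 4 (quality of life) names perceived stress, work performance and burnout.
- **Programme.** Section II(1) lists HIIT among the kinds of exercise video, alongside stretching, strengthening, balance and other options. Section II(2) has menus chosen for each person. Section II(3) speaks of "implementing a daily routine of 3 to 8 brief exercise sessions" and a 12-week intervention.
- **Risk at entry.** Section VI exclusion (1) covers "Pregnant individuals, due to safety concerns related to exercise intensity and physical assessments". Exclusion (4) covers "Individuals assigned to high-intensity exercise who have unstable cardiac conditions".
- **Contacts.** Section VII.2(3): "Post-intervention assessment: Within one week following the intervention, participants will complete follow-up assessments". Section VII.2(4): "Follow-up check: One month after the completion of the program, participants will be contacted to assess whether they have continued engaging in the exercises". The same sentence adds that this continued exercise would be independent and not supervised by the research team.
- **Control.** Section IV.1 marks the study as "Uncontrolled".

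**The concern.** For an exercise study, the not-applicable entries for the test drug and for pharmacokinetics are natural. Safety is different. An exercise programme can cause harm, and the selection criteria show that the authors had this in mind when deciding who may take part. The entry in V.2 then sets safety aside once people are enrolled.

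Pain is a good example. Section II(1) aims videos at neck, shoulder, lower-back and lower-limb discomfort, and exclusion (3) removes only people whose limb-joint pain is severe enough to interfere with testing. People with neck or back pain, or milder limb pain, can enrol. A flare is foreseeable, yet pain is not among the outcomes named in section V.

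What is at stake is the balance of the report. If fitness or stress scores improve, a reader will want to know how many participants were hurt, or stopped because of a symptom. How events are tabulated can be left to a SAP. Whether anyone is asked cannot, because data that were never collected cannot be analysed.

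**Working it through.** The synopsis gives no safety figure to reproduce, and no event rate or number of subjects is legible. The check is therefore a reading of each place where an event could be named, asked about or analysed.

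1. **Outcomes named in section V.** Item 1 gives 2 (fitness, functional movement) and item 4 gives 3 (stress, work performance, burnout): 2 + 3 = 5. Events among them: 0. Item 2, the natural place for events, is entered as not applicable. Since events would not be expected under efficacy or quality of life, the 0 of 5 mainly confirms that nothing elsewhere in section V makes up for item 2.

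2. **Steps in section VII.2.** There are four:

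| Step | Stated content | Stated to ask about events? |
|---|---|---|
| (1) Pre-intervention assessment | Baseline testing | No |
| (2) Intervention period | 12-week programme | No |
| (3) Post-intervention assessment | Follow-up assessments, not itemised | No |
| (4) One-month contact | Whether exercise has continued | No |

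Events stated: 0 of 4. These are one-line entries in a summary, so the count shows what is stated here, not what will be done.

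3. **Analysis in section IX.1.** The heading mentions both efficacy and safety, but this may be template wording. The text below it covers normality checks, paired comparisons before and after, and correlations. No weight is placed on this, because a SAP could supply the tabulation.

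4. **Sections V.2 and VI side by side.** Exclusion (1) gives safety as its reason, for pregnant individuals. Exclusion (4) bars unstable cardiac conditions in those assigned to high-intensity exercise. It is conditional: it shows that such assignment is foreseen, not how many will receive it. Criteria that lower risk at entry can stand beside a plan with no safety outcome, so the sections fit poorly but do not contradict each other.

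5. **Could harm show up elsewhere?** Worsening on the fitness, functional, stress, work or burnout measures could still be seen at the post-intervention assessment. A fall, an injury that healed, a cardiac symptom or the reason someone stopped would not be identified from those measures. The gap is therefore limited to events.

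**The case against.** The strongest reply is that this is a synopsis. Section VII is headed as a summary and asks for brief descriptions, so silence there proves little. Reporting under local ethics rules may exist outside it. The wording of VII.2(4), which sets later exercise apart as unsupervised, suggests some supervision during the 12 weeks, and events might come to light then. HIIT is one choice in a personalised menu that also offers stretching and balance work, and the objectives make no safety claim.

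Most of this stands, and it rules out several stronger readings:

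- **That the study has no way of learning about events.** The document supports only that none is shown here. The form of any supervision is not described, and event collection during it is neither shown nor excluded.
- **That sections V.2 and VI contradict each other.** They do not, for the reason given in the check.
- **That the number of prescribed sessions measures the risk.** Three to eight a day over 12 × 7 = 84 days gives 252 to 672 sessions if daily means seven days a week. That counts brief sessions of every type as prescribed, with no adherence figure and no share for HIIT. It does not measure the gap.
- **That oversight is absent because the data safety monitoring board item shows no answer.** The tick marks there cannot be read, so nothing follows.

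The objection does not explain the entry itself. V.2 is not silent: it states that safety does not apply, in a list whose efficacy and quality-of-life items were filled in for an exercise study.

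**Conclusion.** The point holds in limited form, as a worthwhile and cheap improvement. V.2 records a choice not to assess safety in a programme whose options include high-intensity exercise, and nothing else in the synopsis names an event outcome or a question about events. No stated objective or planned test fails. Followed as written, the entry leaves any benefit to be reported without a count of injuries, pain flares, falls, cardiac symptoms or withdrawals caused by them.

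The size can be given only as coverage: 0 of 5 named outcomes and 0 of 4 procedure steps, both from a summary document. No event rate or interval is offered, because the inputs are not legible. The conclusion assumes that no fuller text already provides for event collection. If one does, the remedy reduces to correcting V.2 so that it agrees with that text.

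**What to change.** Replace the entry in V.2 with participant-reported adverse events (injury, new or worse pain, falls, cardiac symptoms) and the reason for stopping the programme.

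- **When to ask.** Ask at the post-intervention assessment and at the one-month contact, both already planned, and at any contact that already takes place during the 12 weeks. State the period each question covers.
- **Whom to ask.** Include participants who stopped early, where they can be reached. Someone who missed the post-intervention assessment can be asked about the programme at the one-month contact.
- **What to report.** Give the number and proportion with an event among those asked, and the number not reached. Do not count those not reached as event-free.
- **How to word it.** Describe the events without attributing them to the programme, since there is no control group.

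The cost is a few extra questions, some attempts to reach early leavers and one descriptive table. The downside is recall: minor events are likely to be under-reported, so their counts should be presented as a lower limit. The change concerns data collection only and leaves the exercise programme and its clinical management as they are.

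### The only cardiac exclusion listed, VI.2 (4), applies only to people assigned to high-intensity exercise, yet every participant takes the physical tests before and after the intervention

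*Protocol*

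**What the plan says.** Everything relevant is in the protocol synopsis.

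- **Cardiac exclusion.** VI.2 (4) excludes "Individuals assigned to high-intensity exercise who have unstable cardiac conditions", with angina, myocardial infarction and heart failure as examples.
- **Other main exclusions.** VI.2 (1) excludes pregnancy, "due to safety concerns related to exercise intensity and physical assessments". VI.2 (2) excludes diagnosed neurological disorders and gives no reason. VI.2 (3) excludes severe limb-joint pain "that interferes with their ability to complete the assessments".
- **Who is tested.** VI.1 (2) admits people who are "Willing to participate in a 12-week exercise intervention, complete related questionnaires, and undergo physical performance assessments".
- **When they are tested.** VII.2 (1): "Participants will undergo baseline testing within one week prior to the start of the exercise intervention". VII.2 (3): "Within one week following the intervention, participants will complete follow-up assessments". Neither line makes an exception by menu.
- **What is tested.** V.1 gives only "Physical fitness assessments, Performance on functional movement tasks". It names no test and no level of effort.
- **What is screened before testing.** VII.1 (3): "Participants will complete the informed consent form and attend a brief interview to complete questionnaires". The content described is basic information, such as exercise habits, and an assessment of personal problems and exercise needs, from which the menu is designed. Cardiac history is not mentioned.
- **Range of menus.** II (1) covers stretching, strengthening, cardiorespiratory endurance, balance, HIIT and movement skills. Endurance work and HIIT are separate items.

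**The concern.** An exclusion criterion decides who enters a study. Exclusion (4) instead decides which exercise a person with an unstable cardiac condition may be given, because it takes effect only on assignment to high-intensity exercise. The physical tests are a second source of exertion, and everyone takes them. The criterion does not reach them. Nor does it clearly reach endurance work offered outside the high-intensity category.

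What is at stake is participant safety. By writing (4), the sponsor has judged that people with unstable cardiac conditions should not do high-intensity exercise. If any of the fitness tests calls for comparable effort, the listed criteria allow those same people to take it, provided that their menu is a milder one. The analysis in section IX is not affected.

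**Working it through.** No arithmetic applies beyond counting, and the plan gives no figure to reproduce. The check sets the criteria against the procedures.

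1. **Count the exclusions.** VI.2 lists 4. Three of them, (1), (2) and (3), apply whatever the menu. One, (4), is cardiac, and it is the only one that depends on the menu.

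2. **Count the physical tests.** VII.2 has 2 rounds, baseline (1) and post-intervention (3). The one-month check in VII.2 (4) asks whether people are still exercising and is not described as a physical test, so it is not counted. VI.1 (2) makes willingness to be tested a condition of entry, and no line exempts any menu.

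3. **Apply the criteria to one case.** Take an employee with unstable angina whose needs assessment leads to a neck-and-shoulder stretching menu.
   - (1) pregnancy: not met.
   - (2) neurological disorder: not met.
   - (3) severe limb-joint pain: not met.
   - (4) unstable cardiac condition with high-intensity assignment: the condition is present and the assignment is not, so not met.

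   The person is eligible and goes through both test rounds. The same holds if the menu contains cardiorespiratory endurance videos that the team does not class as high-intensity. The synopsis does not define that class.

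4. **Look for anything that offsets this.** The interview in VII.1 (3) mentions no cardiac history. VII.2 mentions no exemption from testing. V.2 marks safety criteria as not applicable. Nothing shown closes the gap.

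5. **Ask what can be said about size.** The synopsis gives neither the tests nor their intensity, the number-of-subjects field shows no figure, and there is no prevalence of unstable cardiac disease among the staff. Neither the number of people affected nor the risk per test can be derived. An assumed prevalence would at most give the chance that such a person is present, not the chance of harm from testing, so none is offered.

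**The case against.** The strongest reply has four parts.

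**It is a synopsis.** The list is headed as the main criteria, and the procedures are marked as a summary. Further criteria or test-day precautions may exist in a fuller document. This stands as a limit: a reader might infer that the study has no cardiac screening at all, and the synopsis does not show that. It does not remove the point, because the complaint is about a condition written into a stated criterion.

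**The condition is deliberate.** Menus run from stretching to HIIT, and tying the cardiac rule to the demanding menu lets people with heart disease use gentle ones. That is a fair reason for the exercise part of the rule. It does not cover the tests, which are the same for everyone as far as the text shows.

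**The tests may be mild.** This stands. A reader might infer that the tests are hazardous for cardiac patients, but V.1 does not say how strenuous they are.

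**The other exclusions prove less than they seem to.** A reader might take exclusions (1) and (3) as showing that the sponsor regards the assessments as unsafe in general, so that (4) contradicts them. The text does not go that far. Exclusion (1) gives the assessments as a safety reason for pregnancy only. Exclusion (3) is about being able to complete the tests, not about danger. Exclusion (2) does not mention them. Extending the reasoning of (1) to cardiac disease is a reasonable inference, but it is the reader's inference.

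**Conclusion.** The point holds as a gap in the listed criteria, not as a contradiction and not as a demonstrated hazard. One of the 4 main exclusions is cardiac. It is limited to high-intensity assignment, while 2 rounds of physical testing apply to all, and menus without HIIT may include cardiorespiratory endurance work. Followed as written, the list admits and tests a person with an unstable cardiac condition who is on another menu.

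The size of the risk is unknown because the exertion of the tests is not stated. The conclusion rests on two readings: that the testing in VII.2 applies to every participant, as its unqualified wording says, and that no offsetting screen exists outside the text shown. If a fuller document already screens for cardiac disease before testing, what remains is to align the wording of (4) with it. The change is worth making because it is specific, concerns participant safety and costs very little.

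**What to change.** Delete the condition on assignment from VI.2 (4), so that it excludes all individuals with unstable cardiac conditions whatever their menu, and keep the three examples already given. Add a cardiac-history question to the consent interview in VII.1 (3), and state that the answer is checked before baseline testing. Rewording alone may not be enough, since the interview as described asks nothing from which the criterion could be applied.

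The cost is one edited criterion, perhaps one added question at an interview that already takes place, and the loss of a few volunteers who could have followed a mild menu. If the sponsor wants to keep those volunteers, the alternative is a separate rule that exempts them from exertional tests or adapts the tests. That requires the synopsis to say which tests are exertional, and it leaves some participants with incomplete or non-comparable outcome data. The unconditional exclusion is simpler and does not depend on what the tests turn out to be, provided that the cardiac history is actually asked.

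### Does calling the data cross-sectional in section IX undermine the planned analyses of a before-and-after study?

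*Protocol*

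**What the plan says.** Section IX, item 1, begins: "This study adopts a cross-sectional data collection approach". It then sets out two kinds of efficacy analysis.

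- **Paired comparison.** If the data are normal, "parametric tests such as the paired-sample t-test will be used to compare pre- and post-intervention differences"; otherwise a Wilcoxon signed-rank test is used.
- **Correlations.** As an addition, "correlations between variables will be analyzed using either" a Pearson or a Spearman coefficient, depending on normality. The sentence does not name the variables or the visit, and does not say whether levels or changes are meant.

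The rest of the Protocol describes repeated measurement. Section VII, 2(1): "Participants will undergo baseline testing within one week prior to the start of the exercise intervention". Section VII, 2(3): "Within one week following the intervention, participants will complete follow-up assessments". Section VII, 2(4) adds a contact one month after the programme. Objective (3) in section II is to run the 12-week programme "and to evaluate changes in staff" health, work performance and exercise behaviour. Section IV marks the study as uncontrolled.

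**The concern.** A cross-sectional study measures each person once. This one measures each participant before and after a programme, so the opening sentence of section IX contradicts sections II and VII and the paired tests that follow it.

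The paired test states its own time points and so overrides the label. The correlation sentence states none. An analyst who took the label at its word might correlate fitness with work performance at one visit and present the result as evidence about change. The two quantities differ: staff who are fitter may report better performance at every visit even if gaining fitness brings no gain in performance. A looser reading would stack the before and after records as separate observations, which would make the p-values too small. At stake would be a misleading secondary result in a study whose interest is in change.

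**Working it through.** The Protocol text at hand gives no sample size, standard deviation or correlation, and no figure is in dispute, so there is nothing to reproduce. The check has two parts.

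**1. Which planned analyses depend on the label?**

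| Text | What it fixes | Governed by the label? |
|---|---|---|
| Section VII, 2(1) and 2(3) | Tests within one week before and one week after the programme | No; it contradicts the label |
| Objective (3) | Whether outcomes change over 12 weeks | No |
| Section IX, paired t-test or Wilcoxon | Before-to-after differences within a person | No; the time points are in the sentence |
| Section IX, correlations | Choice of coefficient only | Not stated |

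Only the correlations are open. The label describes how the study collects data. It does not say which values enter a correlation, and the schedule in section VII corrects it for every analysis alike.

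**2. Could the choice matter? (assumed inputs throughout)**

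*Algebra.* Take equal variances, within-measure correlation between visits ρ, correlation between the two measures at the same visit r, and between the two measures across visits c. Then

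corr(change X, change Y) = (r − c)/(1 − ρ).

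With ρ = 0.8 and r = 0.5:

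- c = 0.50: 0.00/0.20 = 0.00
- c = 0.45: 0.05/0.20 = 0.25
- c = 0.40: 0.10/0.20 = 0.50
- c = 0.30: 0.20/0.20 = 1.00

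All four correlation matrices are valid, so a one-visit correlation of 0.5 fits a change correlation anywhere from 0 to 1.

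*Simulation.* Each measure is a stable part plus a visit-specific part, with before-after correlation 0.7 (range 0.5 to 0.9), n = 50, a two-sided 5% Pearson test and 10,000 trials per setting.

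- Stable parts correlated 0.5, changes unrelated: the one-visit correlation is 0.7 × 0.5 = 0.35, significant in 72% of trials (42% to 92%); the change correlation is 0, significant in 5%.
- Stable parts unrelated, changes correlated 0.5: the one-visit correlation is 0.3 × 0.5 = 0.15, significant in 18% (43% down to 6%); the change correlation is significant in 97%.
- No association, two records per person stacked: the variance is inflated by 1 + 0.7² = 1.49, and the false-positive rate is 11% (8% to 15%).

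*What change scores cost.* If half the within-person variance is measurement error, a true change correlation of 0.5 is seen as 0.5 × 0.5 = 0.25, significant in about 42% of trials at n = 50.

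These figures show that level and change correlations answer different questions in any two-visit study. None of them comes from this trial, and none measures an effect of the label. The stacking case is not even a literal reading, because cross-sectional means one record per person and stacking needs two. The paired test is the same in every scenario.

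**The case for a change.** The strongest case for a change is that this is a false statement and not an omission. A statistical analysis plan that described the design correctly would disagree with the Protocol. The label is also the only general description of the data in section IX, it sits above an analysis with no time point of its own, and replacing it would cost a sentence.

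Part of this stands: the word is wrong, no extraction gap or redaction explains it, and the correlation sentence leaves the choice among baseline, post-programme and change values open.

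The rest does not. Objective (3) asks whether outcomes change, not whether changes in different outcomes move together; the paired test answers it. The correlations are assigned to no objective, so they cannot be faulted for failing to serve that one. A label that yields to the schedule for the paired test cannot be treated as binding for the next sentence. Once it is set aside, what is left is an unstated time point for a supplementary analysis, which a protocol commonly leaves to the statistical analysis plan; that document was not available here. Requiring change scores would be a preference: single-visit correlations among stress, burnout and fitness are legitimate, and change scores pay for their relevance in measurement error. The title, "Effects of an Exercise Snack Intervention on Employee Health and Work Performance", has no bearing on this point.

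**Conclusion.** The label is a clerical slip. The design is plainly a single-group before-and-after study without a control group, and a reader can see that from sections II, IV and VII and from the paired tests. Correcting the word would be tidy, but it changes no planned test, estimate or data item, so the effect on the analysis of objective (3) is nil.

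The open choice for the correlations is ordinary detail that an analyst fills by naming the visit or the change score. Choosing between them is a trade-off between relevance to change and precision. This conclusion rests on reading the correlations as supplementary, as section IX introduces them. If they were later presented as the evidence on change, the values used would have to be stated, and the simulated contrasts would then describe a real risk, with sizes that depend on the assumed n of 50 and before-after correlation of 0.5 to 0.9.

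### The normality gate names the one-sample Kolmogorov-Smirnov test without a correction for estimated mean and SD; uncorrected, it misses most non-normality at small to moderate n, with modest effect on the final tests

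*Protocol*

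**What the plan says.** Protocol section IX.1 names one normality test: "The normality of continuous variables will be assessed using the One-Sample Kolmogorov-Smirnov test". Its result is binding: "Based on the results of the normality test, appropriate statistical methods will be selected". If normality is not rejected, "parametric tests such as the paired-sample t-test will be used to compare pre- and post-intervention differences"; otherwise "non-parametric tests such as the Wilcoxon signed-rank test will be employed". The same verdict decides between Pearson and Spearman for the correlations.

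On computation the section says only that "all data analyses will be conducted using SPSS version 20". It gives no reference mean or SD, no correction for estimating them and no significance level for the check. It does not say whether raw scores or within-person changes are tested. The number of subjects (section IV, item 8) carries no figure in the text at hand.

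**The concern.** The ordinary null distribution of the one-sample Kolmogorov-Smirnov (K-S) statistic holds only when the reference normal curve is fully specified beforehand. No such curve is given for these fitness, stress, work-performance and burnout measures, so mean and SD must be estimated from the sample being tested. The fitted curve then lies too close to the data, and the usual p-value is too large.

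A gate that almost never rejects gives little protection. A report that normality was confirmed would carry little weight, and outcomes better served by a rank method would stay with the t-test or Pearson.

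**Working it through.** The plan gives no figure of its own to reproduce.

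**Inputs.** From section IX.1: the named test and the rule that follows from it. Assumed, because the text gives none: an uncorrected p-value, a 5% level for the check, n from 20 to 200, and the shape of the data.

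**Step 1: why the level collapses.** The statistic is D = max|F_n(x) − Φ((x − m)/s)|, with m and s the sample mean and SD. The uncorrected large-sample rule rejects when √n·D exceeds 1.358, since 2·exp(−2 × 1.358²) = 2·exp(−3.688) = 0.050. The simulated 95th percentile of D with m and s estimated is the Lilliefors cut-off.

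- n=30: uncorrected cut-off 1.358/√30 = 0.248; Lilliefors 0.158.
- n=100: uncorrected cut-off 1.358/√100 = 0.136; Lilliefors 0.089.

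**Step 2: true level under normality** (200,000 to 400,000 normal samples per n, nominal 5%).

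| n | Large-sample p-value | Exact p-value |
|---|---|---|
| 20 | 0.005% | 0.008% |
| 30 | 0.007% | 0.012% |
| 50 | 0.010% | 0.013% |
| 100 | 0.011% | 0.015% |
| 200 | 0.013% | 0.016% |

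As a control, the same code with known mean and SD gave 4.98% to 5.10%, so estimating the parameters causes the loss.

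**Step 3: detection of skewed data**, uncorrected K-S vs Shapiro-Wilk.

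| Distribution | n=30 | n=60 | n=100 |
|---|---|---|---|
| Gamma shape 4 (skewness 1) | 0.3% vs 45% | 2% vs 78% | 7% vs 96% |
| Gamma shape 2 (skewness 1.4) | 2% vs 75% | 10% vs 98% | 33% vs 100% |
| Exponential (skewness 2) | 9% vs 97% | 49% vs 100% | 92% vs 100% |

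The Lilliefors form detects 26%, 47% and 78% at n=30, and 69%, 95% and 100% at n=100. At n=200 even uncorrected K-S rejects skewness 1.4 in 87% of samples.

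**Step 4: consequence for the pre-post test.**

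- *Exponential changes with zero mean.* The paired t-test's type I error is about 7% at n=30, 6% at n=60 and 5.8% at n=100.
- *Symmetric heavy-tailed changes (t with 3 df, shift 0.3 SD).* Replacing the K-S gate by the corrected one raises the rule's power from 49% to 56% at n=30 (56 − 49 = 7 points) and from 75% to 86% at n=60 (86 − 75 = 11 points). Type I error stays near 5%.
- *Skewed changes sent to Wilcoxon.* With a true mean change of zero at n=60, Wilcoxon rejects about 15% of the time for gamma shape 2 and 26% for exponential changes. It addresses the (pseudo-)median, which is not zero there, so these are not pure error rates; they show that the question has changed.

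**The case against.** **The uncorrected p-value is assumed.** The protocol neither states nor excludes a Lilliefors correction. How SPSS 20 computes the p-value cannot be read from the document, and an SAP not shown might settle it. This stands, and the 0.01% is therefore conditional. But the protocol itself names the plain test and makes it binding, so the ambiguity is worth removing there.

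**A reader might infer that clearly skewed outcomes are always passed as normal.** The documents do not support that. It depends on n, which the text at hand does not give, and on the degree of skewness: at n=100, skewness 2 is caught 92% of the time.

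**A reader might also infer a large loss of power in the correlations.** For a lognormal pair (log-SD 1, underlying correlation 0.35) at n=60, Pearson has 49% power and Spearman 74%. That comparison does not describe the plan's rule. On such data even uncorrected K-S flags at least one variable in about 98.5% of samples. The rule then has about 73% to 76% power if either flag leads to Spearman, and 69% to 71% if both are needed. With log-SD 0.5, where K-S often misses, the gap is only 70% vs 75%. The example is no evidence of harm.

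**The benefit for the change tests is mixed.** This stands too. The t-test tolerates skewness fairly well, nothing in the document shows that the changes are strongly skewed, and a sharper gate sends more outcomes to a test with a different null hypothesis.

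**Conclusion.** The point holds in a limited form and is minor. As named, with mean and SD estimated and no correction, the check runs at about 0.01% instead of an assumed 5%. It misses most skewness of 1 to 2 at n=30 and most skewness of 1 to 1.4 at n=60; exponential data at n=60 are missed about half the time. By n=100 strong skewness is mostly caught.

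The damage to the final tests is small: type I error of about 6% to 7% for exponential changes, and 7 to 11 points of power for symmetric heavy-tailed changes, both at n=30 to 60. These sizes rest on the assumed n, 5% level, uncorrected p-value and distributions, none of which the protocol fixes.

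**What to change.** In section IX.1, wherever a normality check is kept, replace the one-sample K-S test by the Shapiro-Wilk test or the Lilliefors-corrected K-S test. State that it is applied to the within-person change for the pre-post comparison, and to each of the two variables for a correlation. Add that a Wilcoxon result will be reported as a shift in the (pseudo-)median, not in the mean.

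This changes a sentence or two and needs no extra data. The price is that more outcomes will be analysed by ranks, and for skewed changes those results no longer concern the mean change. Fixing the analysis in advance, without a normality pre-test, would make the point moot.
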